[figure not shown]

[figure not shown]

### 3.0 Introduction

This Statistical Analysis Plan (SAP) describes the statistical methods that will be used during the analysis and reporting of data collected under BioCryst Pharmaceuticals, Inc., Protocol BCX4430-106.

This SAP should be read in conjunction with the study protocol and electronic case report form (eCRF). This version of the SAP has been developed using the protocol dated 11-Jan-2019 and the final eCRF(s) dated 30-Oct-2018.

An approved and signed SAP is a requirement for database lock.

This SAP covers all results that will be processed by the PRA Early Development Services (EDS) Biostatistics Department.

PRA EDS will perform the final pharmacokinetic (PK) and safety and tolerability analyses.

This SAP supersedes the statistical considerations identified in the protocol; where considerations are substantially different, they are identified. Any post-hoc or unplanned analyses, or substantive changes from the planned analysis in this SAP performed to provide results for inclusion in the clinical study report (CSR), will be clearly identified in the CSR. Changes to planned analyses do not require an updated SAP but should be denoted in the CSR if significant.

### 4.0 Changes from Previous Version of Approved SAP

Not applicable. This is the first version of the SAP.

### 5.0 Study Objectives

#### 5.1 Primary Objective

The primary objective of the study is:

- To evaluate the safety and tolerability of single ascending doses (SAD) of galidesivir (BCX4430) administered by intravenous (IV) infusion in healthy subjects.

#### 5.1.1 Primary Endpoints

The primary endpoints of the study are:

- Safety and tolerability parameters including adverse events (AEs) and serious adverse events (SAEs), laboratory abnormalities, vital signs, electrocardiograms (ECGs), echocardiograms (ECHOs), cardiac telemetry, and physical examination (PE).

#### 5.2 Secondary Objective

The secondary objective of the study is:

- To characterize the plasma pharmacokinetic (PK) profile and urinary elimination of SAD of galidesivir administered by IV infusion in healthy subjects.

#### 5.2.1 Secondary Endpoints

The secondary endpoints of this study are:

- The PK parameters for galidesivir, including: maximum concentration ( $C_{max}$ ), last measurable concentration of drug ( $C_{last}$ ), time to maximum concentration ( $T_{max}$ ), area under the concentration time curve from time zero to last time ( $AUC_{last}$ ), area under the concentration time curve from time zero to infinity ( $AUC_{inf}$ ), clearance (CL), volume of distribution ( $V_z$ ), percentage of AUC extrapolated between  $AUC_{last}$  and  $AUC_{inf}$  ( $AUC_{extrap}$ ),  $\lambda_z$ , and half-life ( $t_{1/2}$ ), and other parameters, where appropriate.

- Dose proportionality of galidesivir based upon  $AUC_{inf}$ , AUC from time 0 to time "t" ( $AUC_t$ ), and  $C_{max}$ .

## 6.0 Study Design

[figure not shown]
This SAD study will evaluate the safety, tolerability, and PK of single doses of galidesivir vs. placebo administered as IV infusions in healthy subjects enrolled in up to four dose cohorts of 8 subjects each, for a total of 32 subjects. A single dose of study drug will be administered per cohort: 6 subjects will receive galidesivir IV, and 2 subjects will receive matching placebo.

The planned cohorts are as follows:

- Cohort 1, Regimen A: 5 mg/kg galidesivir or placebo, IV infusion × 1 dose
- Cohort 2, Regimen B: 10 mg/kg galidesivir or placebo, IV infusion × 1 dose
- Cohort 3, Regimen C: 15 mg/kg galidesivir or placebo, IV infusion × 1 dose
- Cohort 4, Regimen D: 20 mg/kg galidesivir or placebo, IV infusion × 1 dose

Subjects will be randomized within each cohort to receive either galidesivir or placebo. As a safety precaution, on the first day of dosing in each cohort, only 2 subjects will be dosed (to be referred to as sentinel subjects). The randomization schedule will be constructed such that 1 of the sentinel subjects dosed on the first day will be randomized to receive galidesivir and 1 will be randomized to receive placebo. After review of the safety data from the 24-hour post-dose period for the sentinel subjects, which includes review of any AEs, any abnormalities in the bedside ECGs, safety laboratory assessments and vital signs, the remainder of the cohort (5 subjects randomized to galidesivir; 1 randomized to placebo) will be dosed at least 2 days after the sentinel subjects.

Enrollment of subjects in each sequential higher dose level cohort will occur only after completion of a clinical safety review of laboratory, AE, vital sign, ECG (12-lead and telemetry), and PE data for all subjects up through 96 hours post-dose and plasma PK data through 24 hours post-dose. Based upon safety review and evaluation of the data for each subject, adjustments in the dose escalation scheme for the next cohort may be made, including omission of higher dose cohorts in the event that the safety and PK parameters have been adequately characterized with lower dose cohorts. Where considered appropriate to meet the study objectives, adjustments in the protocol-specified dose escalation for subsequent cohorts are permissible (i.e., an intermediate dose between the previous tolerable dose and the scheduled next higher dose). The study design is shown in Figure 1 (below).

**Figure 1 BCX4430-106 Study Design**

Abbreviations: D = day; PK = pharmacokinetic.

## 6.1 Sample Size Considerations

No formal power or sample size calculations were used to determine cohort sizes. Cohort sizes were based upon experience in other SAD Phase 1 studies. A sample size of 6 subjects receiving active drug per cohort should provide adequate characterization of PK and safety assessments within this setting.

## 6.2 Randomization

This is a double-blind study; treatment assignment within a cohort will be blinded to the PI, clinical staff, study subjects, and the data management team, with the exception of the unblinded dosing team, if required. The randomization schedules will be generated by an unblinded study statistician. A computer-generated randomization schedule will be used to randomly assign subjects to galidesivir or placebo. Subjects in each of the Cohorts 1 to 4 will be randomized to galidesivir or placebo in a 3:1 ratio (ie, 6 subjects per cohort will be randomly assigned to receive galidesivir and 2 subjects per cohort will be randomly assigned to receive placebo). As a safety precaution, on the first day of dosing in all cohorts, 2 sentinel subjects will be initially dosed, and the randomization schedule will be generated so that in each cohort 1 sentinel subject is randomly assigned to receive galidesivir and 1 sentinel subject is randomly assigned to receive placebo. The remainder of the cohort will be randomized such that 5 subjects are assigned to receive galidesivir and 1 subject assigned to receive placebo.

Following confirmation of eligibility, subjects will be identified by a unique 5-digit subject identifier (e.g., 11001) in which the first digit indicates the study site identifier, the second digit indicates the cohort number and the final 3 digits indicate the subject number. Any replacement subjects will be identified by replacing the third digit "0" with "9". For example, if Subject 11005 withdraws from the study early, the replacement subject will be numbered 11905 and will receive the same study treatment (i.e., active or placebo) as Subject 11005.

Subject numbers will be as follows:

Cohort	Subject Numbers	Replacement Subject Numbers
1	11001 to 11008	11901 to 11908
2	12001 to 12008	12901 to 12908
3	13001 to 13008	13901 to 13908
4	14001 to 14008	14901 to 14908

## 7.0 Overview of Planned Analysis

### 7.1 Changes from Protocol

There are no changes from the protocol.

### 7.2 Interim Analysis and Key Results

An interim PK report will be prepared by Biocryst for review by the DEC that will document the following PK findings for each dose cohort:

- Preliminary plasma PK parameters (through 24-hours post-dose) based upon nominal times: AUC;  $C_{max}$ ,  $T_{max}$ , terminal elimination half-life ( $t_{1/2}$ ; median, minimum, maximum, geometric mean, coefficient of variation [CV%])
- Predictions of  $C_{max}$  and AUC values for the next cohort, where relevant

### 7.3 Final Analysis

Draft TFLs will be provided after database lock. After Sponsor comments have been incorporated, the TFLs will be finalized and incorporated into the first draft of the CSR.

## 8.0 Data Review

### 8.1 Data Management

Data handling and transfer will take place under the PRA Data Management Plan for the study.

### 8.2 Acceptance of Data for Summarization

Programming of analysis datasets and TFLs may be ongoing during the data management of the study. However, programming of analysis datasets and TFLs will be completed and quality controlled (QC'd) after

database lock. Only quality-assured results released by the Safety Laboratory, Bioanalytical Laboratory, or other external data source will be used for the programming of analysis datasets and TFLs for the final report. Any data values requiring investigation or corrections that are identified while programming the analysis datasets and TFLs will be sent to the project Data Manager. If the issue affects the TFLs the Programmer or Statistician who identified the issue will follow it to resolution.

## 9.0 Definitions and General Analysis Methods

### 9.1 Analysis Data Presentation

#### 9.1.1 Rounding

In listings, data will be presented with the same precision as the original data. Derived data will be rounded for presentation purposes.

For all summaries, minimum (min) and maximum (max) will be presented to the same number of decimal places as the original data, the mean and median to 1 decimal greater than the original data, and the standard deviation (SD) to 2 decimals greater than the original data. Frequency percentages and percent coefficient of variation (CV%) will be presented to 1 decimal.

PK parameters will be rounded in the derived datasets as determined by the pharmacokineticist and presented as such in the listings. Each parameter will have a fixed number of decimals ( $C_{max}$  and AUC will have 3 significant figures, and half-life and  $T_{max}$  will have 1 decimal). In general, the pharmacokineticist will use discretion when deciding the number of decimals for each parameter.

#### 9.1.2 Imputation

Unless otherwise noted, data will not be imputed.

#### 9.1.3 Descriptive Statistics

Unless otherwise indicated, continuous variables will be summarized with the following descriptive statistics: n (number of observations), (arithmetic) mean, SD, min, median, and max.

Categorical data will be summarized with frequencies and percentages. Percentages by categories will be based on the number of subjects exposed within a treatment. Percentages will be rounded to 1 decimal, except 100% which will be displayed without any decimal places. Percentages will not be displayed for zero counts. Categories will be presented in the tables exactly as they appear in the eCRF / database.

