4.4.1. Study and Population

Healthy subjects have been selected to minimize variability in factors that may affect the safety, tolerability, and PK profile of galidesivir. In MVD outbreaks, both sexes are affected; therefore, both men and women will be enrolled in the study. It is considered imperative to characterize the safety and PK of galidesivir in women, including those of reproductive age, at this early stage

of development, and therefore considered acceptable to include women in this study, using the strict contraception requirements that are specified in Section 8.1. Both genders will be enrolled in the study.

Reproductive toxicology studies have been conducted (Section 4.2.3). Women of childbearing potential may be enrolled in this study if they meet the contraceptive and pregnancy test requirements listed in the inclusion and exclusion criteria.

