11.3.1.7. Clinical Laboratory Screening and Safety Assessments

Blood and urine samples will be obtained per the schedule of assessments (Table 5). Screening inclusion laboratory tests are listed on Table 6. A list of all laboratory tests that will be performed during the study are provided in Table 8. Laboratory assessments do not require fasting conditions. Acceptable windows for collection of blood samples for laboratory assessments are the same as for the PK samples. Urinalysis (post dose) has an acceptable window of \pm 2 hours from the nominal time as designated in Table 5. Samples will be collected into appropriate tubes as specified by the clinical laboratory.

Study eligibility is partially determined by screening laboratory tests. Inclusion laboratory test results must be within acceptable eligibility range for all labs listed in Table 6 at Screening. For all clinical laboratory safety assessments, the laboratory results values obtained on Day -1 establish the baseline for chemistry, hematology, and coagulation laboratory safety results.

Results for Cystatin C, NGAL, and free testosterone (males only) do not need to be obtained prior to initiation of dosing. These tests will be used for baseline measurements for post-dose comparison for evaluation of renal and testicular health following administration of galidesivir.

At time points when multiple samples are taken, the samples will be taken in the following order to minimize the risk of K EDTA contamination of the biochemistry samples.

1. Coagulation
2. Biochemistry / testosterone
3. PK
4. Hematology

Laboratory values drawn after study drug dosing should be assessed within 12 hours of receipt by the PI or qualified designee. Safety laboratory assessments can be taken anytime post-dose on Days 1 to 5 to fit with the clinic and lab schedule. Results from safety laboratory assessments are not required for completing assessments on the following day. Any laboratory findings outside of the normal range should be documented and described in the source documentation. Results from baseline and on-treatment clinical chemistry, hematology, coagulation, and urinalysis tests will be provided to the Sponsor for real-time review.

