Bilirubin* Glucose Leukocytes* Ketones* Nitrites* pH* Protein [#] Urobilinogen* Presence of blood microscopy if dipstick is abnormal (at the discretion of the PI)	Prothrombin time (PT)/international normalized ratio (INR) Activated partial thromboplastin time (aPTT) Hepatitis B surface antigen, hepatitis C antibody, HIV type 1* [#] Total Testosterone (male subjects only)* Free Testosterone (male subjects only)* Troponin I* CK-MB Cystatin C* Urine Albumin-to-Creatinine ratio (UACR)* Neutrophil gelatinase-associated lipocalin (NGAL)*

*Analytes without established DMID toxicity criteria

[#]Analytes that are used for screening laboratory tests per Sections 8.1 and 8.2

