### 17.1.3 Laboratory Data

Clinical laboratory data will be presented using units from the study data tabulation model (SDTM) Controlled Terminology.

A descriptive statistics summary of continuous laboratory results and derived changes from baseline for cardiac markers, chemistry, coagulation, hematology, and urinalysis will be provided by cohort and scheduled timepoint.

Laboratory abnormalities outside of the normal laboratory reference ranges and associated grades (according to study specific DMID criteria specified in the 2014 DMID Adult Toxicity Grading Scale in Appendix 5) should be denoted where possible. For those analyte results that are out of the normal range and do not have an established DMID toxicity criteria, the severity grading will be provided by the PI. The number and percentage of subjects experiencing treatment-emergent graded toxicities will be summarized.

A shift table describing the change in continuous clinical laboratory values from baseline to follow-up (number and percentage of subjects) will also be provided. The following categories will be used: Normal, DMID Grade 1, DMID Grade 2, DMID Grade 3, DMID Grade 4.

All laboratory data will be listed by subject, including laboratory variables not listed in the protocol.

A separate listing of out-of-range values will also be provided. Normal ranges will be used directly from the clinical laboratory and will be included in the listings for reference. Flags for high and low values will be provided in the listings.

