- b. A physical examination consisting of the head and neck, skin, chest (lungs and heart), abdomen (gastrointestinal tract, liver, spleen and kidneys), back, musculoskeletal system, and neurologic system should be conducted at screening and on Day 4 prior to discharge. Breast and genitourinary system do not require examination unless the potential subject indicates a complaint or comorbidity that could result in exclusion. All other physical exams will be symptom directed. The site of infusion should be checked for any changes in skin.
- c. Three (3) serial ECGs will be performed at screening and baseline 1–3 minutes apart. Pre-dose ECG should be collected within  $\leq 2$  hours of the first dose.
- d. 12-lead ECGs will be conducted on Day 1 at 2 and 4 hours post dose (post start of the infusion) and on Day 2 at 24 hours post dose. An acceptable window is  $\pm 10$  minutes from the nominal time point. All subsequent ECGs are daily.
- e. Cardiac telemetry will be initiated  $\geq 2$  hours prior to administration of the dose and will continue for 24 hours after the infusion is started. Subjects may be disconnected for bathroom, hygiene needs, and for 20-minute periods 3 times a day for meals. In addition, subjects may be disconnected for 10 minutes every 2 hours while awake for mild physical exercise such as walking or calf exercises.
- f. The ECHO may be performed at any time from screening to Day -1 for eligibility determination. An ECHO should also be performed on Day 3. An acceptable window for the Day 3 ECHO is up until Day 4 discharge.
- g. Vital signs (except temperature) will be obtained pre-dose (within 2 hours of dosing) 1, 2, 4, and 8 hours post dose (post start of the infusion) on Day 1, at 24 hours post dose on Day 2 and once per day where indicated. Oral temperature will be obtained at 8 hours post dose on Day 1 and at 24 hours post dose on Day 2. Subjects should be rested for 10 minutes in the supine position prior to vital sign measurements.
- h. A serum pregnancy test will be administered at screening to all women; all other pregnancy tests performed during the study may be urine pregnancy tests.
- i. An FSH level will be measured in women who report that they have been postmenopausal  $\leq 2$  years.
- j. Free testosterone will be measured in male subjects.

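### SAP 9.1.3 divides categorical counts by all subjects exposed, so any percentage for a test done only in men, such as testosterone, is too low in groups that include women

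*SAP*

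**What the plan says.** SAP 9.1.3 gives one denominator for categorical data: "Percentages by categories will be based on the number of subjects exposed within a treatment". The opening qualifier in that section, which allows for exceptions, is attached to continuous variables. The same section adds: "Percentages will not be displayed for zero counts".

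For laboratory data, SAP 17.1.3 plans that "The number and percentage of subjects experiencing treatment-emergent graded toxicities will be summarized", and names no other denominator. For out-of-range analytes that "do not have an established DMID toxicity criteria, the severity grading will be provided by the PI". Protocol Table 8 marks testosterone as one of these analytes.

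The SAP's schedule of assessments says "Free testosterone will be measured in male subjects"; Protocol Table 8 also restricts it to men. Protocol 4.4.1 says "Both genders will be enrolled in the study".

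Protocol 11.3.1.7 says of cystatin C, NGAL and free testosterone: "These tests will be used for baseline measurements for post-dose comparison for evaluation of renal and testicular health following administration of galidesivir". It leaves their analysis to the SAP, with out-of-range values graded by their multiple of the limit of normal. The interpretation is to weigh how many subjects are affected, the clinical course and the contrast with placebo.

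**The concern.** The numerator for a testosterone abnormality can come only from men, but the stated denominator includes women who were never tested. The printed figure is therefore not the rate among those at risk of being counted. It also moves with the number of women in each group, which has nothing to do with the drug.

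Safety is the primary objective. Protocol 4.2.3 reports testicular toxicity in the rat, and Protocol 4.5 gives testosterone as the planned monitoring in men. Because Protocol 11.3.1.7 relies on the number of subjects affected and on the placebo contrast, those are the two readings the denominator disturbs. SAP 9.4.2 plans no covariates, so no other analysis would separate the sexes.

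**Working it through.** **Group sizes.** The SAP (section 6.0) plans four cohorts of 6 galidesivir and 2 placebo subjects: 4 × (6 + 2) = 32, which matches its stated total. SAP 9.1.4 pools placebo, so N = 6 for each dose and N = 4 × 2 = 8 for placebo. This assumes that all planned subjects are dosed and none is replaced.

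**Formula.** Let x be the number of men with a treatment-emergent graded abnormality, m the number of men tested and N the number exposed.

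- Percentage under SAP 9.1.3: 100 × x/N
- Percentage among those tested: 100 × x/m
- Ratio of the first to the second: (x/N) ÷ (x/m) = m/N

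The ratio is below 1 whenever m < N. If x = 0, no percentage is printed and there is nothing to distort.

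**One affected man, galidesivir group of 6.** The number of men is not given in the documents, so the range is shown.

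| Men tested (m) | SAP rule, 1/6 | Among tested, 1/m | Ratio m/6 | Highest percentage the SAP rule can print |
|---|---|---|---|---|
| 6 | 16.7% | 16.7% | 1.00 | 100% |
| 5 | 16.7% | 20.0% | 0.83 | 83.3% |
| 4 | 16.7% | 25.0% | 0.67 | 66.7% |
| 3 | 16.7% | 33.3% | 0.50 | 50.0% |
| 2 | 16.7% | 50.0% | 0.33 | 33.3% |
| 1 | 16.7% | 100% | 0.17 | 16.7% |

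In pooled placebo, one affected man always prints as 1/8 = 12.5%. With 6, 4 or 2 men tested, the rate among them is 16.7%, 25.0% or 50.0%.

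**Comparisons between groups.**

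- Between doses, same rate in men: 1 of 2 men and 2 of 4 men are both 50%, but print as 1/6 = 16.7% and 2/6 = 33.3%.
- Against placebo, same rate in men: 1 of 2 men in a dose group prints as 16.7%; 3 of 6 men in pooled placebo prints as 3/8 = 37.5%. Both are 50% among those tested.
- Reversed order: 2 of 3 men on drug (66.7%) prints as 2/6 = 33.3%, below 3 of 8 (37.5%) in an all-male placebo group.

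**How often a dose group includes a woman.** If each subject is independently male with probability p, the chance of at least one woman among six is 1 − p⁶. That is 1 − 0.5⁶ = 0.984 at p = 0.5 and 1 − 0.75⁶ = 0.822 at p = 0.75. Both values of p are assumptions.

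**The case against.** The strongest objection is that the SAP names no testosterone percentage. In the SAP text available, testosterone appears only in the Appendix 2 schedule. It is absent from the safety variables in 17.1, from the laboratory groups summarised in 17.1.3 and from the listing titles. It reaches Table 14.3.5.3 only through the general rule that the investigator grades analytes without DMID criteria. A reader might infer that the SAP specifies a testosterone table with a wrong denominator; the documents do not support that. What stands is that the general rules admit such a percentage, Protocol 11.3.1.7 expects grading and a count of subjects affected, and nothing in the SAP would then correct the denominator. That the protocol leaves testosterone analysis to a SAP that does not name it is a separate gap, which a denominator edit would not close.

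Other limits also hold:

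- **Recoverable from other outputs.** Counts are printed beside percentages, laboratory data are listed by subject and sex is tabulated by cohort, so a careful reader could rebuild x/m. Any continuous summary of testosterone would carry its own n. This reduces the harm but does not make the printed percentage right.
- **Shells.** They are a separate document and may already define another denominator. If so, they conflict with 9.1.3, and the text still needs correcting.
- **Shift and QTcF tables.** A reader might infer that these are biased too. The shift table uses DMID grades, which testosterone lacks. For other parameters the exposed denominator matters only where values are missing. The documents give no missing-data rate, and subjects stay in the unit for 96 hours.
- **False dose trend.** A reader might infer that one is likely. That would need both an uneven sex mix, which the documents do not give, and abnormal men in the groups compared. No probability can be attached.
- **Testes as a main target.** Protocol 4.2.3 names kidney and liver as the primary rat targets, with testes among the others and not listed in the monkey. Protocol 4.5 names the kidneys as the principal target after IV infusion.

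**Conclusion.** The point holds as a wrong general rule with a narrow effect. Applied as written, SAP 9.1.3 would turn any percentage of subjects with a treatment-emergent graded testosterone abnormality into the rate among tested men times m/N. The direction is certain whenever a group includes a woman and at least one man is abnormal. The size is not: for a dose group of 6 with 5 down to 2 men, the printed figure is 0.83 down to 0.33 of the rate among those tested. Comparisons across doses and with pooled placebo are unreliable when the sex mix differs.

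This rests on testosterone entering Table 14.3.5.3 through the general laboratory rules, on the shells not overriding 9.1.3, and on groups of 6 and 8 as planned. It should be corrected before the tables are run, but it does not threaten the study's safety conclusions, because counts and listings remain available.

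**What to change.** In SAP 9.1.3 or 17.1.3, add a rule along these lines:

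- Treatment-emergent graded laboratory toxicities: the denominator is the subjects in that treatment with a baseline and at least one post-baseline result for the analyte; for sex-specific tests, the tested subjects of that sex. Print this n.
- Laboratory shifts and QTcF change-from-baseline categories, where values are missing: subjects with a baseline and a value at that timepoint.
- Absolute QTcF categories, where values are missing: all subjects with a value at that timepoint, with no baseline required. Otherwise a subject with a post-dose value above 500 msec but no baseline would be dropped.
- AE, disposition and exposure tables: keep the exposed denominator.

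The baseline condition for graded toxicities fits Protocol 12.3.1.3, which defines treatment-emergent grades by an increase from baseline.

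The change needs SAP wording and, if the shells follow 9.1.3, edits to the affected laboratory and QTcF shells. It needs no new data. The drawback is that denominators vary by row, which is why n must be printed.
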